14.4 Missing, unused & spurious data

All analysis will be performed on complete cases. No imputation of missing data will be carried out. Further detail will be provided in the Statistical and Health Economics Analysis Plan (SHEAP).

14.5 Termination of the study

here will be no formal 'stopping rules' or 'discontinuation criteria' for individual participants, parts of the trial and entire trial. Any decision to terminate the trial will be reached by the SSC in discussion with the study's funder.

14.6 Inclusion in analysis

All randomised participants' data will be included in the analysis.

15 Analysis

15.1 Main analysis

As this is a feasibility study, the analysis will be descriptive in nature. Continuous data will be reported as means and standard deviations, or medians and interquartile ranges, as appropriate. Categorical data will be reported as frequencies and proportions. All data will be reported both overall, per arm, and by setting type. Outcomes will be estimated with their associated 95% confidence intervals. No formal hypothesis testing will take place.

The study will be reported in accordance with the CONSORT extension for randomised pilot and feasibility studies.

Exploratory analysis of outcome measures to be used in the main trial will be based on the ITT principle, and will compare mean scale scores at 12-months between arms by fitting two-level linear regression models, with pupils nested within schools. The model will adjust for baseline scores, region (England or Scotland), and school size. Results will be reported as adjusted mean differences and 95% confidence intervals, focussing on effect sizes and their precision rather than p-values. Intra-cluster

correlation coefficients will be reported with associated 95% confidence intervals, with sources of variation explored using both quantitative and qualitative data.

We will also fit regression models to explore baseline factors associated with intervention receipt and retention in the study at the 12-month follow-up time points. Findings will be reported and may be used to inform study design modifications required in the main trial.

A detailed Statistical Analysis Plan will be written and signed off prior to undertaking any analysis.

15.1.1 Sub-group & interim analysis

No sub-group or interim analyses will take place.

15.2 Qualitative analysis

With appropriate consent, all interviews will be audio-recorded, transcribed fully, and anonymised for analysis. Computer software (NVivo) will be used to manage the qualitative data and transcripts. Thematic analysis will be used to analyse each of the sub-sets of interviews (school leaders, class teachers, trainers, pupils, parents/carers) separately and independently. We will then also use a thematic analysis approach for a qualitative synthesis across the interview sub-groups. Finally, a triangulation exercise will be conducted combining all of the qualitative results with the quantitative data analysis results including an assessment of potential barriers and facilitating factors (gathered from all data sources) that may need to be taken into account in a future definitive trial, including recruitment strategies, implementation fidelity, intervention mechanisms and their interaction with local context. Data collection across the feasibility study will be designed to maximise the potential for triangulation.

Qualitative analysis will follow three stages. First, we will use a coding framework to thematically analyse each transcript. Second, for each identified theme we will summarise and interpret key findings for each group of interviewees (e.g. all data coded to 'recruitment' within teacher interviews). Third, we will compare main findings from each theme for all interviewee groups (e.g. key findings from teachers, parents and pupils on recruitment). No formal synthesis will take place, rather we will compare findings for each interviewee group, using the written summaries of each theme (for each group of interviewees), and where necessary going back to the coded data. Comparison of findings across the multiple interviewee groups will aid completeness of analysis (e.g. where an issue is only covered in one set of interviews) and understanding the degree of alignment across different groups of participants. Assessment of feasibility of intervention components/implementation and trial procedures will be aided by understanding the extent to which teachers, parents and pupils share a broadly similar perspective on acceptability/feasibility. Where findings across interviews are divergent this will be important in helping us to incorporate the views of different groups, and to identify where we might make changes to these aspects of the trial.

15.3 Health Economics

The health economic component of this study will include two main elements. The first will involve an estimation of intervention costs, including costs of development, training, supervision, and delivery of Zippy's Friends intervention sessions.

The second component will involve assessing the feasibility of collecting data on broader health service utilisation and health-related quality of life of children with ID. For health service use, this will involve modification and testing of an appropriate version of the child and adolescent service use schedule (CA-SUS) to collect data on health service utilisation. We will assess respondents' understanding of the questions and modify the wording or add explanation if anything is unclear. We will also assess the measure's comprehensiveness in capturing all relevant services as testing may identify items which are redundant or important services that have been omitted. For health-related quality of life, we will assess completion rates and item missingness for proxy report versions of generic paediatric quality of life measures EQ-5D-Y and CHU-9D. These measures allow the calculation of Quality Adjusted Life Years (QALYs) and would be used as the primary outcome measure for cost-effectiveness analysis in a subsequent full RCT.

16 Data Management

Source Data is defined as "All information in original records and certified copies of original records of clinical findings, observations or other activities in a clinical study necessary for the reconstruction and evaluation of the study. Source data are contained in source documents." There is only one set of source data at any time for any data element, as defined in site source data agreement.

Study data

	CRF	Encrypted voice	SAE data
		recordings	
Outcome			
measures	Х		
Interviews			
		X	
		~	
Adverse events			
			Y
			~

16.1 Data collection

All outcome data will be entered into a secure, encrypted bespoke online database developed by the clinical trials unit, based on paper or electronic copies of the measures completed by participants. Fidelity checks and data cleaning will be performed as detailed in the data management plan, and according to CTR SOPs (GCP and GDPR compliant). Electronic data will be stored on Cardiff University servers and access will be password protected (restricted only to those who need direct access, who will be provided with individual log-ins). Paper copy forms will be stored in locked filing cabinets at participating sites and destroyed following data entry.

We will aim to make research data available wherever possible and in line with the NIHR position on sharing data, such that the sharing of research data must: protect the confidentiality and privacy of individuals; respect the terms of consent by individuals who are involved in research; be consistent with relevant legal, ethical and regulatory frameworks; and guard against unreasonable costs.

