12.1 Assessments

Participants will be recruited, assessed at baseline and randomised in the 2021 summer term. The intervention (ZF-SEND) to commence in September of the 2021 Autumn term and continue into the summer term until end the summer term 2022. Post-intervention assessments and qualitative interviews will be completed from May to July 2022. Therefore, all participants (children, teachers and parents/carers) are involved in this study for approx. 12 months.

Children will be seen twice (baseline and post-intervention) for an assessment session with one of the RAs. They will complete the 'Me and My School' questionnaire and two quality of life measures (EQ5D-Y and CHU-9D) with the help of the RA.

Teachers will be asked to complete (for each child participating in the research) three questionnaires: the Nisonger Child Behavior Rating Form (NCBRF), the Strengths and Difficulties Questionnaire (SDQ) and the Emotional Literacy Assessment. They are required to complete these questionnaires during the two assessment periods (baseline and post-intervention) and can choose whether to complete on-line or paper copies. The presence of an RA is not required. Each set of questionnaires (per child) takes approx. 20 minutes to complete and teachers are paid £10 for each set completed.

Parents/carers will be asked during each of the two assessment periods (baseline and postintervention) to complete one set of questionnaires for their child which consists of 5 questionnaires: the parent/carer-rated Strengths and Difficulties Questionnaire (SDQ), the Emotional Literacy Assessment, the two parent/carer-rated Quality of Life (EQ5D–Y and CHU–9D) measures and the Service use parent/carer-rated modified Child and Adolescent Service Use Schedule (CASUS). Parents will be given various options for how to complete these measures: 1/paper copies sent by post; 2/ on-line; 3/ telephone interview with RA; 4/ face-to-face interview with RA. Each set of questionnaires takes approx. 40 minutes to complete. A subsample (N=10 -12) of all three participant groups (children, parents/carers and teachers) will be interviewed as part of the process evaluation (see section 12.2 below) during the follow-up assessment phase (autumn term 2021).

Figure 1 presents the schedule of assessments.

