16.2 Completion of CRFs

All assessments and data collection will be completed using either web-based or paper-based CRFs.

Where possible, assessments should be completed using the web-based CRFs. If paper-based CRFs are used, the research assistant will enter these data on a web-based CRF at the earliest opportunity. All outcome measures are completed by participants at baseline and upon completion of the intervention which will be about 12 months follow up post-randomisation. All CRFs will be administered to participants at site by the RA/s.

In accordance with the principles of GCP, the CI is responsible for ensuring accuracy, completeness, legibility and timeliness of the data reported to the CTR in the CRFs. CRF data will be checked for missing, illegible or unusual values (range checks) and consistency over time.

If missing or questionable data are identified, a data query will be raised on a data clarification form. The data clarification form will be sent to the RA by email. The response to the data query should be completed on the data clarification form. Any paper-based CRFs should not be altered. All answered data queries and corrections should be signed off and dated by the RA at each site. The completed data clarification form should be scanned and returned to the CTR by email. A copy of the original data clarification form should be retained at the participating site along with the participants' CRFs. The CTR will send reminders for any overdue data. It is the participating site's responsibility to submit complete and accurate data in timely manner.

Detailed plans for data entry and handling are located in the study specific Data Management Plan and will be stored in the TMF.

17 Protocol/GCP non-compliance

The Chief Investigator should report any non-compliance to the study protocol or the conditions and principles of Good Clinical Practice to the CTR in writing as soon as they become aware of it.

18 End of Study definition

The end of study is defined as the completion of the follow-up data collection from the final participant. Once the final report has been approved by the study funder, a copy will be sent to the UoB. A summary report of the study will be provided to the REC within one year of the end of the study.

UoB must notify the main REC of the end of a clinical study within 90 days of its completion or within 15 days if the study is terminated early.

19 Archiving

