All data will be kept for 10 years in line with CTR Research Governance Framework Regulations for clinical research. This data will be stored confidentially on password protected servers maintained on the Cardiff University Network. Files will only be accessible to researchers responsible for the running of the study and the CI. All procedures for data storage, processing and management will comply with the General Data Protection Regulation 2016. All paper records will be stored in a locked filing cabinet, with keys available only to researchers and the CI. The Study Statistician will carry out the analyses. All essential documents generated by the study will be kept in the Study Master File.

20 Regulatory Considerations

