22.1 Monitoring

The clinical study risk assessment has been used to determine the intensity and focus of central and on-site monitoring activity in the Zippy's Friends study. Low+ monitoring levels will be employed and are fully documented in the study monitoring plan.

Investigators should agree to allow study related monitoring, including audits and regulatory inspections, by providing direct access to source data/documents as required. Findings generated from on-site and central monitoring will be shared with the UoB, CI and CTR.

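### Section 16.1 has paper outcome forms destroyed after data entry, but the query procedure in section 16.2 still needs them then

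*Protocol*

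**What the plan says.** Section 16.1 (Data collection) states: "Paper copy forms will be stored in locked filing cabinets at participating sites and destroyed following data entry". The only trigger it names is data entry.

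Section 16.2 (Completion of CRFs) describes what happens to paper data: "If paper-based CRFs are used, the research assistant will enter these data on a web-based CRF at the earliest opportunity". The CRF data are then checked for missing, illegible or out-of-range values and for consistency over time. Queries are emailed to the research assistant, who answers and signs them off. Paper CRFs are not to be altered. On filing, the section says: "A copy of the original data clarification form should be retained at the participating site along with the participants"; the sentence ends by naming those participants' CRFs.

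Paper is a real route. Under section 12.1, teachers "can choose whether to complete on-line or paper copies", and for parents: "Parents will be given various options for how to complete these measures: 1/paper copies sent by post".

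Three other places bear on the point:
- The opening of section 16 counts original records and certified copies as source data, and adds: "There is only one set of source data at any time for any data element, as defined in site source data agreement".
- Section 22.1 commits investigators to monitoring, audits and inspections "by providing direct access to source data/documents as required".
- Section 19 says "All data will be kept for 10 years", describes that storage as password-protected servers, and separately says that all paper records go into a locked cabinet.

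**The concern.** For a questionnaire filled in on paper, the paper is the original record. Once it is gone, what remains is a transcription with nothing to compare it to. A blank in the database may mean that the respondent left the item out, or that the person entering the data missed it. The two can be separated only by looking at the form.

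That distinction matters more here than in many trials. Whether children, teachers and parents complete the measures is one of the feasibility questions in section 5.3 (question 9). Section 15.3 plans to assess completion rates and item missingness for the EQ-5D-Y and CHU-9D, which parents may complete on paper. Section 14.4 analyses complete cases without imputation, so a value that cannot be recovered may also cost a case. Destruction cannot be undone if a problem comes to light later.

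**Working it through.** The protocol gives no figure to reproduce, so the check sets the sections side by side in the order in which a paper form would meet them.

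1. **Completion.** A teacher or parent completes a paper questionnaire (section 12.1). Section 16.2 prefers web forms where possible but allows paper.
2. **Entry.** The research assistant enters it as early as possible (section 16.2).
3. **Destruction.** Section 16.1 allows the form to be destroyed once it is entered. No date is given. Neither section makes destruction wait for query closure, a source check, a scan or database lock.
4. **Checks.** Section 16.2 then has the CRF data checked. Two of these checks sit badly with step 3:
   - Illegibility is a property of a handwritten page, not of a typed value.
   - Consistency over time needs both assessments. Figure 1 puts baseline in May to July 2021 and post-treatment in May to July 2022, so a baseline value may first be questioned about a year after it was collected.
5. **Queries.** The research assistant must answer. For a paper form, the natural evidence is the form itself.
6. **Filing.** The clarification form is kept at site with the CRFs, and paper CRFs stay unaltered. Both rules presuppose that a paper CRF still exists.

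A site that acts on step 3 as soon as its trigger is met cannot carry out steps 5 and 6 for paper forms. This is the direct conflict.

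Two further comparisons are weaker:
- **Section 22.1.** Access to source fails only if a visit falls after destruction and no certified copy was made. No section of the protocol provides for such a copy.
- **Section 19.** The 10-year period is tied to data on servers, which the electronic database could satisfy. The sentence on storing all paper records covers outcome forms as worded, but gives paper no period of its own and could have been meant for other papers, such as consent and assent forms.

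**Size.** Only a ceiling can be given. Section 12.1 lists 3 child, 3 teacher and 5 parent questionnaires, so 11 per child per time point, and section 14.3 plans 96 children.
- Full follow-up: 96 × 11 × 2 = 2,112 questionnaires.
- With the 75% follow-up assumed in section 14.3 (0.75 × 96 = 72): 96 × 11 + 72 × 11 = 1,056 + 792 = 1,848.
- Teacher and parent questionnaires only, the ones for which section 12.1 offers paper: 8 × (96 + 72) = 1,344.

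These count all planned questionnaires, however completed. The protocol states no paper share, so the number exposed could lie anywhere from none up to these totals.

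**The case against.** The strongest reply is that following data entry need not mean at once. The same paragraph of section 16.1 says that checks and cleaning follow the data management plan and the trials unit's procedures, and that forms are held in locked cabinets first. Section 16.2 also sends the detail of data handling to the data management plan, and the opening of section 16 leaves the definition of source to a site agreement. Neither document is shown, and either may require scanning or a source check before destruction. The paragraph can therefore be read as enter, check, clean, then destroy.

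Part of this stands. The protocol does not say that forms are destroyed immediately, and it would be wrong to conclude that no verification is planned. But entry is the only condition the protocol states, and a supporting document that adds others would not remove the conflict between sections 16.1 and 16.2.

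A reader might also infer more than the text supports:
- **That the archive rule is plainly broken.** It is not, because the 10-year period is described for data on servers.
- **That monitoring access is necessarily lost.** It is lost only after destruction without a certified copy.
- **That the only source for the outcomes disappears.** This can apply only to measures completed on paper, not to those entered online.
- **That a known, large number of forms will be unverifiable.** Without a paper share this cannot be said, and a form may have been checked before it was destroyed.
- **That the SDQ standard deviation or intracluster correlation will be distorted.** The documents give no entry error rate, so no such effect can be shown.

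**Conclusion.** The point holds as a contradiction within the protocol, confined to paper-completed measures. Section 16.1 states a destruction rule triggered by entry, and section 16.2 states query and filing rules that need the form after entry. Section 22.1 and the paper-records sentence in section 19 add to the case for reconciling the wording, but do not carry it alone.

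The consequence is loss of the means to resolve a later query, and so of the ability to separate respondent non-completion from entry omission. That touches the completion and item-missingness results directly. Its size cannot be estimated from the documents. The conclusion assumes only that some teachers or parents use the paper option and that section 16.1 is applied as written. It does not depend on any of the form counts.

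**What to change.** In section 16.1, replace the destruction clause with a retention rule along these lines: paper outcome forms, or certified copies made before any destruction, are kept in locked storage at least until all data queries are closed, any source checks are done and the database is locked.

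In section 19, state whether paper outcome forms or their certified copies fall under the 10-year archive period. The documents do not settle this, and the sponsor should decide it explicitly. If the data management plan or site source data agreement already sets such steps, a cross-reference in section 16.1 would help, provided the unconditional clause is removed.

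The cost is two sentences of wording, plus short-term secure storage or scanning of paper forms from 12 schools. Longer storage follows only if section 19 is made to cover them. The change should be in place before the first paper forms are entered, since a destroyed form cannot be recovered.

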16.2 Completion of CRFs

All assessments and data collection will be completed using either web-based or paper-based CRFs.

Where possible, assessments should be completed using the web-based CRFs. If paper-based CRFs are used, the research assistant will enter these data on a web-based CRF at the earliest opportunity. All outcome measures are completed by participants at baseline and upon completion of the intervention which will be about 12 months follow up post-randomisation. All CRFs will be administered to participants at site by the RA/s.

In accordance with the principles of GCP, the CI is responsible for ensuring accuracy, completeness, legibility and timeliness of the data reported to the CTR in the CRFs. CRF data will be checked for missing, illegible or unusual values (range checks) and consistency over time.

If missing or questionable data are identified, a data query will be raised on a data clarification form. The data clarification form will be sent to the RA by email. The response to the data query should be completed on the data clarification form. Any paper-based CRFs should not be altered. All answered data queries and corrections should be signed off and dated by the RA at each site. The completed data clarification form should be scanned and returned to the CTR by email. A copy of the original data clarification form should be retained at the participating site along with the participants' CRFs. The CTR will send reminders for any overdue data. It is the participating site's responsibility to submit complete and accurate data in timely manner.

Detailed plans for data entry and handling are located in the study specific Data Management Plan and will be stored in the TMF.

17 Protocol/GCP non-compliance

The Chief Investigator should report any non-compliance to the study protocol or the conditions and principles of Good Clinical Practice to the CTR in writing as soon as they become aware of it.

18 End of Study definition

The end of study is defined as the completion of the follow-up data collection from the final participant. Once the final report has been approved by the study funder, a copy will be sent to the UoB. A summary report of the study will be provided to the REC within one year of the end of the study.

UoB must notify the main REC of the end of a clinical study within 90 days of its completion or within 15 days if the study is terminated early.

19 Archiving

All data will be kept for 10 years in line with CTR Research Governance Framework Regulations for clinical research. This data will be stored confidentially on password protected servers maintained on the Cardiff University Network. Files will only be accessible to researchers responsible for the running of the study and the CI. All procedures for data storage, processing and management will comply with the General Data Protection Regulation 2016. All paper records will be stored in a locked filing cabinet, with keys available only to researchers and the CI. The Study Statistician will carry out the analyses. All essential documents generated by the study will be kept in the Study Master File.

20 Regulatory Considerations

